This study is a randomized controlled trial using a 2:1 study randomization ratio. The treatment group will receive an e-cigarette and nicotine pods for six weeks and are encouraged to make a complete switch from combustible cigarettes to e-cigarettes. The study will consist of three in-person visits (baseline, week 2, and week 6) in which measurements are conducted and behavioral support is provided to the e-cigarette group. Phone calls will be scheduled between the visits (week 1 and week 4) to confirm appointments, collect data on tobacco use, and to support switching to e-cigarettes (e-cigarette group only).

[figure not shown]

Figure 1. Study Timeline.

Informed Consent. The informed consent will be reviewed by having the researcher read the consent form out loud. The participant will be given time to read the informed consent form and ask questions. It will be made clear in the consent form that the participant has the option to take more time to consider their desire to participate in the study and reschedule at a later date, or to decline to participate at any point. The study begins once the participant signs the consent form, indicating understanding of the procedures, requirements, and consent.

Incentives. Participants will be compensated for their time during the lab visits at escalating increments of \$20 at baseline, \$40 at week 2, and \$60 at week 6, totaling up to \$120. Participants in the e-cigarette group are instructed that full compensation is contingent upon bringing back their used and unused pods to their next visit. At week 2 and week 6, \$20 of compensation is contingent upon bringing back pods. Those in the e-cigarette group have the opportunity to participate in a follow-up phone assessment six months after enrollment, entailing an additional \$20 compensation.

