Urine: cotinine ng/mL, creatinine mg/mL, nitrosamine 4-(methylnitrosamino)-1-(3-pyridyl)-1-butanol (NNAL) pg/mL, and 3-hydroxycotinine ng/mL

Saliva: Cytokine Panel and C-Reactive Protein

Nasal Swab: MMP9 ELISA in pg/mL and TGF-B1 ELISA in pg/mL

X. Study Visits Overview

Baseline	Week 1	Week 2	Week 4	Week 6
Participant consent	Follow-up check-in	Urine test	Follow-up check-in	Saliva sample (San Diego)
Saliva sample (San Diego)	Yesterday tobacco use	Blood pressure test (must be less than 160/105)	Yesterday tobacco use	Urine test
Complete contact sheet		Carbon monoxide test		Blood pressure test
Blood pressure test (must be less than 160/105)		Eligibility check		Carbon monoxide test
Carbon monoxide test (must be greater than 5 ppm)		Follow-up check in sheet (EC group)		Nasal swab (Kansas City)
Nasal swab (Kansas City)		Timeline follow back		Weight
Final eligibility check and Study ID assignment		Spirometry test		Follow-up check in sheet (EC group)
Randomization		Week 2 survey		Timeline follow back
Charge JUUL (EC group)		Collect used JUUL pods (EC group)		Spirometry test
Timeline follow back		Provide more JUUL pods (EC group)		Week 6 survey
Pod count form (EC group)		Schedule visits/phone calls		Collect used JUUL pods (EC group)
Height and weight		Compensation		Tobacco cessation referral
Baseline survey part 1				Exit survey
Spirometry test				Compensation
Baseline survey part 2				
Cigarette questions and breathing conditions				
E-cigarette switching fact sheet (EC group)				
E-cigarette use instructions (EC group)				
E-cigarette trial and subjective effects questionnaire (EC group)				

Baseline action planning (EC group)				
Schedule visits/phone calls				
Reimbursement schedule				
Urine test				
Compensation				

Table 3. Surveys and tests by study timepoint.

At each lab visit, participants will receive compensation and sign a receipt. At the end of the study, participants will be given a referral to the California Smokers' Helpline ([name]) or Kansas Tobacco Quitline ([name]).

XI. Study Questionnaires

Surveys will contain items on demographics, smoking measures, tobacco measures, physiological measures, and psychosocial assessments. Given the possibility of low literacy among participants, surveys will be verbally administered along with visual cue cards.

XII. Data Management

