Missing data will be minimized through extensive training of research staff in addition to follow-up with participants. Data will be entered into REDcap electronically and paper forms (biological measures and pod count forms) will be stored in participant files. Paper forms with identifiable information such as consent and contact information will be stored in a separate, locked location. TLFB data will be entered into excel, with paper calendars and data entry forms stored in participant files. REDcap entry will happen after the lab session and will be audited and checked by project managers daily. REDCap is a secure, HIPAA-compliant, web-based application designed to support data capture for research studies. All protocol-specified data will be linked by unique subject ID, assigned at randomization. Paper files will be stored on site in a locked filing cabinet and any forms with identifying information (consent form and contact sheet) will be kept in a separate location. Data is only accessible to personnel involved with this research. Access is limited by the research facility being locked at all times.

XIII. Recording and Reporting of Adverse Effects

Development of any adverse effects will be monitored closely by a project manager such that fields capturing adverse events will be reviewed daily. At each study visit, participants will be asked about the development of any other, new, or worsening symptoms. At each visit and each phone call after the initial visit, participants in the e-cigarette condition will be asked if they were experiencing any barriers to switching to e-cigarettes or any concerns about switching. This open-ended format is intended to capture any unexpected adverse events. Unexpected serious adverse events will be reported to the CSUSM IRB and assessed by the PI to determine if related to e-cigarette use, and if so, reported to the NIH and FDA. Participants will be encouraged to contact staff if they have any questions, problems using their e-cigarette, or if any adverse events develop.

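### Adverse events are sought more intensively in the e-cigarette arm than in the control arm, so event rates by arm may be biased upward for e-cigarettes

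*Protocol*

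**What the plan says.** Protocol section XIII sets out two scheduled questions. The first has no arm restriction: "At each study visit, participants will be asked about the development of any other, new, or worsening symptoms". The second is limited by arm and has a wider schedule: "participants in the e-cigarette condition will be asked if they were experiencing any barriers". It covers obstacles to making the switch and worries about it, and it is put at all contacts that follow baseline, whether in person or by telephone. The protocol then states what the second question is for: "This open-ended format is intended to capture any unexpected adverse events".

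Section VI describes the calls: "Phone calls will be scheduled between the visits (week 1 and week 4) to confirm appointments, collect data on tobacco use", with support for switching added for the EC group only. Controls are therefore called too, but safety is not among the stated purposes of the calls.

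Table 3 in section X labels the check-in sheet at the week 2 and week 6 visits as an EC-group item. For the week 1 and week 4 calls it lists a follow-up check-in with no arm label and does not describe its content.

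Section XIII also encourages participants in general to contact staff if an adverse event develops.

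**The concern.** A comparison of adverse-event rates between arms is fair only if events are looked for in the same way in both. Here the question that the protocol itself names as its means of catching unexpected events goes to one arm, and it is asked at two contacts where the other arm has no stated safety question. More questioning tends to produce more reports. If true rates were equal, the EC arm could still show the higher recorded rate, and symptoms in continuing smokers could go unrecorded. An analysis plan cannot repair this later, because events that were never asked about are not in the data.

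**Working it through.** The protocol gives no figure on this point to reproduce. The check is a count of stated questions, followed by an illustration of what the imbalance could do.

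**Step 1: count the stated questions after baseline** (protocol sections VI, X and XIII).

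| Contact | EC arm | Control arm |
|---|---|---|
| Week 1 call | switching prompt | none stated |
| Week 2 visit | symptom question and switching prompt | symptom question |
| Week 4 call | switching prompt | none stated |
| Week 6 visit | symptom question and switching prompt | symptom question |

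Contacts with at least one such question: EC 4, control 2. Occasions on which a question is put: EC 2 + 4 = 6, control 2.

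**Step 2: illustrate the effect on recorded rates.** Let p be the share of true events caught by the symptom question common to both arms. Let q be the share of the remaining events caught by the EC-only prompt. The protocol gives neither, so both are assumptions. With equal true rates per person:

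- share recorded in control = p
- share recorded in EC = 1 − (1 − p)(1 − q)
- ratio of recorded events per person, EC to control = [1 − (1 − p)(1 − q)] / p

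Example with p = 0.7 and q = 0.3: EC records 1 − 0.3 × 0.7 = 0.79, control records 0.70, and the ratio is 0.79 / 0.70 = 1.13.

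| p | q = 0 | q = 0.1 | q = 0.3 | q = 0.5 |
|---|---|---|---|---|
| 0.5 | 1.00 | 1.10 | 1.30 | 1.50 |
| 0.7 | 1.00 | 1.04 | 1.13 | 1.21 |
| 0.9 | 1.00 | 1.01 | 1.03 | 1.06 |
| 1.0 | 1.00 | 1.00 | 1.00 | 1.00 |

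In this model the bias can run only one way, towards more recorded events in EC. Its size runs from nothing to 50% over the assumed range. It vanishes if the visit question already catches everything (p = 1) or if the switching prompt adds nothing (q = 0).

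**Step 3: the same model after the change.** If both arms get the same question at the same contacts, and the EC-only answers stay out of the comparison, the share recorded is the same in each arm and the ratio is 1.00 when true rates are equal.

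**The case against.** The strongest reply is that no stated analysis is harmed. Aims 1 to 3 concern NNAL and other exposure measures, consumption, perceptions and dependence, and no comparison of adverse events by arm appears among them. Section XIII is about monitoring and reporting. Relatedness of an unexpected serious event is judged case by case by the principal investigator, not from arm rates. This stands, and it limits the weight of the point.

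Controls are also not left unasked. They get the symptom question at every visit and can report events themselves. A visit question can pick up a symptom that began around an earlier call, so the calls add only what would have resolved or been forgotten by the visit. This stands too, and it is why the bias may be near zero.

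The prompt concerns switching, so it could not be put as worded to people who are given no e-cigarette. That is true, and it explains why the item is EC-only. It does not explain why an EC-only item should carry the task of capturing unexpected events. A neutral symptom question could be put to both arms.

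Finally, the unlabelled check-in that Table 3 lists at weeks 1 and 4 might include a safety question for controls. Its content is not shown, so this cannot be ruled out. If it does, section XIII should say so, because as written it describes a call prompt for EC participants only.

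**Conclusion.** By a stated rule, adverse-event ascertainment is more intensive in the EC arm: four post-baseline contacts with a stated question against two. Rates by arm may be biased upward in EC, and control events may be under-recorded. The direction follows from the text. The size does not, and the 1.00 to 1.50 range above rests wholly on assumed values of p and q.

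A reader might go further in three ways that the documents do not support.

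- *Event counts will differ by arm even with no true difference.* Counts will differ anyway under 2:1 allocation (120 against 60). The issue is rates per person, and for those only a possible difference can be claimed.
- *Doubling the contacts nearly doubles detection.* With an assumed 10% chance of a report at each contact, one gets 1 − 0.9⁴ = 0.34 against 1 − 0.9² = 0.19. With 5%, it is 0.19 against 0.10. This takes contacts as independent and gives a switching prompt on a call the same yield as a symptom question at a visit. Nothing in the protocol supports either assumption.
- *Rates by arm cannot be interpreted, or the control arm is the only basis for judging relatedness.* The visit question common to both arms gives a usable basis for comparison if answers are recorded by source, and relatedness is assessed case by case.

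The point is a worthwhile, inexpensive improvement to safety capture. It does not touch the primary outcome.

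**What to change.** In section XIII, add one identical, neutral symptom question for both arms at the week 1 and week 4 calls, and use the same wording at the week 2 and week 6 visits. Keep the switching-barriers question for the EC arm, but record its answers in a separate field as an intervention item. State that any comparison of adverse events by arm uses the common question only. In Table 3, state what the check-in at weeks 1 and 4 contains and which arm receives it.

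The cost is one extra item on calls already made to controls and a small form change. No visit, call or participant is added.
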